9.6 Study Drug Termination

The study drug will be discontinued if any of the following conditions are met prior to the study drug treatment period of 12 weeks:

- 1. Patient or clinician request for withdrawal from the study.
- 2. Patients whose sight is determined as deteriorating to the point of a 10 letter drop in sight. The study drug will be stopped and the patient will be offered the current standard care treatment.

Whilst on the study enrolled participants, [i.e. patients with DMO and thick retinas (400 microns or more)] will be receiving the study drug rather than the current standard treatment (currently anti VEGF drugs in the NHS). Patients who wish to withdraw from the study, those in whom sight loss occurs during the duration of the study or those completing the study in who DMO persists, will be offered this standard care treatment.

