10.9 Research Samples/Exploratory Analysis

The remaining part of the blood sample (10.8 above), will be used to test for ARA 290 antibodies and to complete an exploratory analysis to determine levels of inflammatory markers and carbamylated and glycosylated albumin.

The blood sample will be taken prior to ARA 290 administration at baseline, and at least 2 hours after the most recent treatment. Within 30 minutes after collection, the sample will be centrifuged at 3000 rpm for 10 minutes at 4°C. The collected serum will be transferred to transport tubes [2 tubes for ARA 290 antibodies (approximately 0.5 mL per tube), 2 tubes for carbamylated albumin, 2 tubes for glycosylated albumin, and 2 tubes for immune markers (approximately 0.1 mL per tube)] and stored at -80°C.

Patients leaving the study before study completion (i.e. week 12) will have a full evaluation like that being undertaken at the 12 week visit, unless the patient refuses consent for this evaluation to be undertaken.

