12.2 Data Analysis

In participants in whom both eyes are eligible for inclusion into the study, the eye with the better BCVA will be used as the study eye; however data will be collected and evaluated for both eyes.

Given the short time course of the study (12 weeks), drop outs are not expected to occur.

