2. OUTCOME MEASURES

2.1 Primary outcome measure

Changes from baseline to week 12 (+/-7) days in best corrected distance visual acuity.

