3.3 Data verification

Data verification, consistency and range checks will have been performed at the data entry stage by the CTU, as well as checks for missing data (copies can be found in the Trial Master File). Additional range, consistency and missing data checks will be performed, as appropriate, when the analysis is performed (and when the datasets for analysis are constructed). All variables will be examined for unusual, outlying, unlabelled or inconsistent values.

Given the thorough nature of our follow-up procedure we expect the issue of missing data to be relatively minimal. We anticipate high compliance with initial data collection as this is close to the time of patient registration. If any data is missing imputation will not be done.

Any problems with trial data will be queried with the Trial Managers, Data Managers, or statisticians, as appropriate. If possible, data queries will be resolved, although it is accepted that due to administrative reasons and data availability a small number of problems will continue to exist. This will be minimised.

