6. ANALYSIS PRINCIPLES

In participants in whom both eyes are eligible for inclusion into the study, the eye with the better BCVA will be used as the study eye; however data will be collected and evaluated for both eyes.

Descriptive statistics will be used for the evaluation of primary and secondary outcomes. Differences in mean (SD) change from baseline for all the continuous variables investigated including visual acuity, central subfield thickness, area of retinal ischaemia, retinal sensitivity, patient reported outcome scores as well as levels of ARA 290 antibodies. Confidence intervals will also be presented. When data is not normally distributed, median (interquartile range) will be presented.

Adverse events will be presented using counts and percentages. Additionally, the % of participants with 10 or more and 15 or more ETDRS letter gain will be also reported. Data obtained at week 16 would have been similarly evaluated; however no patients required a 16-week visit.

Exploratory analysis in relation to inflammatory markers and carbamylated and glycosylated albumin will also be observed from baseline to the week 12 visit.

If the retinal perfusion image analysis is not available, it may be presented in a later report.

Additional analysis (not specified in the protocol) will be performed to explore the treatment effect in the non-study eye for (a) those patients with DMO in the non-study eye that did not fulfil the criteria for inclusion into the study (e.g. in patients with central retinal subfield thickness of < 400 microns or in patients with non-central involving DMO) and (b) patients with DMO in the non-study eye that fulfilled criteria for inclusion into the study (e.g. ≥ 400 microns).

As the analysis is only descriptive, no imputation or sensitivity analysis will be performed.

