7.4 Trial events

- Change from baseline to week 12 in best corrected distance visual acuity, mean(sd)
- Change from baseline to week 12 in central subfield thickness, mean(sd)
- Change from baseline to week 12 in central retinal sensitivity, mean(sd)
- Change from baseline to week 12 in retinal perfusion, n(%)
- Change from baseline to week 12 Total area of ischaemia, mean (sd)
- Change from baseline to week 12 in tear production, mean(sd) (study eye only)
- Change from baseline to week 12 in patient reported outcomes, mean(sd)
- Change from baseline to week 12 in ARA 290 antibodies, mean(sd)
- Adverse events, n(%)
- % of participants with ≥10 ETDRS letter gain, n(%)
- % of participants with ≥15 ETDRS letter gain, n(%)
- Change from baseline to week 12 in inflammatory biomarkers, mean(sd)
- Change from baseline to week 12 in Carbamylated Albumin, mean(sd)
- Change from baseline to week 12 in Glycosylated Albumin, mean(sd)
- Change from baseline to week 12 in HbA1C, mean(sd)

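### The SAP does not say how patients stopped for a 10-letter loss enter the week-12 BCVA mean, and it bars the sensitivity analysis that would show the effect

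*SAP*

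**What the plan says.** SAP 2.1 defines the primary outcome as "Changes from baseline to week 12 (+/-7) days in best corrected distance visual acuity". SAP 7.4 summarises it as mean and SD, SAP 6 adds confidence intervals, and Table 3.1 of the SAP has columns for baseline, week 12 and change only.

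Protocol 9.6 lists among the reasons to end study drug before 12 weeks: "Patients whose sight is determined as deteriorating to the point of a 10 letter drop in sight". It continues: "The study drug will be stopped and the patient will be offered the current standard care treatment". Standard care is named there as anti-VEGF. BCVA is measured at weeks 4 and 8 (protocol 10.2), so a drop can be seen before week 12.

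On missing values, SAP 3.3 says "If any data is missing imputation will not be done" and SAP 6 says "As the analysis is only descriptive, no imputation or sensitivity analysis will be performed". Protocol 12.4 says the same as SAP 6. Protocol 12.2 adds that "drop outs are not expected to occur".

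Protocol 10.9 provides for early exit: "Patients leaving the study before study completion (i.e. week 12) will have a full evaluation like that being undertaken at the 12 week visit". Refusal by the patient is the one exception given. The SAP does not mention this evaluation. It also defines no analysis set and no rule for values measured after standard care. It does not spell out the denominator for the letter-gain percentages.

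**The concern.** The stopping rule acts on the variable that is being averaged, so the patients affected are those doing worst. Taken literally, the week-12 summary leaves two routes for such a patient. With no BCVA inside the 7-day window, the patient drops out of the mean. If the patient attends week 12, the value may reflect standard care, yet it is reported as change on ARA 290. Provided standard care restores some vision, both routes push the mean upward.

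Calling the analysis descriptive does not remove this, because the mean and its interval are the quantities that shift. There is no control arm in which the same selection would show. Protocol 3.3 argues that improvement could most likely be attributed to ARA 290, and SAP 5 says the data will inform larger studies.

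**Working it through.** **Inputs from the documents.** n = 10, single arm; stop at a 10-letter drop; BCVA at weeks 4, 8 and 12; outcome is change to week 12. The plan states no SD, effect size or stopping rate, so it has no figure to reproduce.

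**Step 1: exact arithmetic.** Let k of 10 patients stop with an exit change of exactly -10, and let the other 10 - k have mean change m.

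- Stopped patients left out: mean = m.
- Exit value used: mean = ((10 - k)m - 10k)/10.
- Difference: (k/10)(m + 10).

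| k | m = 0: left out / exit used | m = +5: left out / exit used |
|---|---|---|
| 1 | 0 / -1.0 | +5.0 / +3.5 |
| 2 | 0 / -2.0 | +5.0 / +2.0 |
| 3 | 0 / -3.0 | +5.0 / +0.5 |

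If a week-12 value r after standard care is used, the mean is ((10 - k)m + kr)/10, which exceeds the exit-value mean by (k/10)(r + 10). That is 1.0 letter per stopped patient at r = 0 and 1.5 at r = +5. With k = 0 all choices agree.

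**Step 2: how often, and how large on average.** Assumptions, none of them in the documents: normal changes with true mean 0; SD of week-12 change 6, 8 or 10 letters; SDs at weeks 4 and 8 equal to sqrt(0.70) and sqrt(0.85) times that; correlation 0.6 or 0.8 between successive visits (its square between weeks 4 and 12); drop counted from baseline; stop if the change is -10 or worse at week 4 or 8. Bias is measured against the mean had everyone continued, which is 0. Two million patients were simulated per row.

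| SD | corr. | % stopped | P(at least 1 of 10) | Stoppers left out | Stoppers set to 0 after standard care | Exit value used |
|---|---|---|---|---|---|---|
| 6 | 0.6 | 5.1 | 0.41 | +0.35 | +0.34 | -0.27 |
| 6 | 0.8 | 4.6 | 0.38 | +0.46 | +0.44 | -0.10 |
| 8 | 0.6 | 12.8 | 0.75 | +1.01 | +0.88 | -0.78 |
| 8 | 0.8 | 11.4 | 0.70 | +1.32 | +1.17 | -0.29 |
| 10 | 0.6 | 20.2 | 0.89 | +1.83 | +1.46 | -1.36 |
| 10 | 0.8 | 18.0 | 0.86 | +2.41 | +1.98 | -0.50 |

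P(at least 1 of 10) = 1 - (1 - p)^10; for example 1 - (1 - 0.128)^10 = 0.75.

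A true gain shrinks the effect. With a +5 letter mean at week 12, reached linearly, and SD 6, leaving stoppers out adds only +0.13 to +0.16 letters and the chance of any stop is about 15%.

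**Step 3: scale.** Assuming a 95% level (the SAP gives none), the t-interval half-width at n = 10 is 2.262/sqrt(10) = 0.715 SD: 4.3 letters at SD 6 and 7.2 at SD 10.

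**Step 4: responders.** With one responder and two stopped patients, an all-participant denominator gives 1/10 = 10.0% and a completer denominator gives 1/8 = 12.5%.

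**The case against.** The strongest reply is that the SAP is silent on the exit evaluation and does not reject it. Using a measured exit value is arguably not imputation, and it removes the upward bias. A reader might infer that the reported mean is certain to favour ARA 290. The documents do not support that. The bias needs at least one patient to trigger the rule, and that patient then has to be left out or measured after standard care. The documents do not report how many did. The row for a drop in visual acuity in SAP Table 4.2 does not show that anyone lost 10 letters.

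Three further points stand:

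- Standard care is offered, so a stopped patient may decline it or be untreated at week 12.
- The SAP reports letter gains as a percentage of participants, which already suggests an all-participant denominator. Inflated responder rates are therefore only a possibility.
- The shift is smaller than the sampling error at n = 10, and no test or go/no-go threshold depends on the mean.

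It is also fair that the plan discloses a good deal: withdrawals (SAP 7.1), reasons for discontinuation and additional treatments (7.3), exclusions from analysis (7.6), and listings of visual outcomes (Appendix 1). A careful reader of the full report could see who stopped. That does not correct the headline mean, and the explicit bar on sensitivity analysis remains a stated rule.

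Finally, the exit value has its own fault. It is taken before week 12 and selected for being low, so it can err against ARA 290. This argues for showing both results.

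**Conclusion.** The concern holds as a gap with a predictable direction of risk. The SAP ties the primary summary to week 12, bars sensitivity analysis, and does not say how patients stopped on the primary outcome are handled. If any patient stops, leaving that patient out favours ARA 290. So does using a value after standard care, provided that care restores some vision.

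Under zero true effect, SD 6 to 10 letters and correlation 0.6 to 0.8, the completer mean is about +0.4 to +2.4 letters, and the chance that at least one of ten stops is 38% to 89%. The size depends on these assumed values, and the bias is zero if nobody stops. What is affected is the reported mean, its interval and possibly the responder percentages. No error rate is at stake.

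**What to change.** In SAP 6 and 7.4:

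1. Replace the sentence that rules out sensitivity analysis.
2. Define the analysis set as all treated patients.
3. Report mean change in BCVA and central subfield thickness two ways: (a) for patients who stop early, using the last value before any other DMO treatment, normally the exit evaluation of protocol 10.9; and (b) using week-12 values only. State in advance which is the headline.
4. Flag any week-12 value measured after standard care.
5. Count early stoppers as not having gained 10 or 15 letters, with all treated patients as the denominator.

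The cost is SAP wording and one derived variable from data the protocol already collects. The downside is that (a) can err against ARA 290, by about -0.1 to -1.4 letters in the model above, so neither result should stand alone. No change to the stopping rule or to standard care is proposed.

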7. ANALYSIS DETAILS

The results of the analyses will be reported following the principle of the ICH E3 guidelines on the Structure and Content of Clinical Study Reports.

7.1 Recruitment and follow-up patterns

- Recruitment by month
- The number of withdrawals

7.2 Baseline Characteristics

- Gender, n(%)
- Age(years), mean(sd)
- Weight(kg), mean(sd)
- Height(m), mean(sd)
- BMI(kg/m²), mean(sd)
- Blood Pressure(mmHg), mean(sd) systolic, diastolic
- Heart Rate(BPM), mean(sd)

- Temperature(degrees Celsius), mean(sd)
- Oxygen saturation(%), mean(sd)
- C peptide(pmol/L or nmol/L), mean(sd)
- HbA1C(mmol/L), mean(sd)
- Glucose(mmol/L), mean(sd)
- Type of diabetes, n(%)
- Liver Function Test, mean(sd)
- Triglycerides, mean(sd)
- Albumin creatinine ratio, mean(sd)
- HDL, mean(sd)
- LDL, mean(sd)
- Study Eye, n(%)
- Co-morbidities
- Ophthalmologic condition

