3.2 Data completion schedule

The following table describes the time points for completion of clinical record forms.

Table 1. Data Completion Schedule

	Screening / Baseline	2 week s	4 weeks	8 weeks	12 weeks	16 weeks*	4 weeks post drug termination**
Consent	✓						
Pregnancy Test	✓						
Medical History	✓		√	√	√	✓	
Medications	✓		√	√	√	✓	
Vital Signs***	✓		√	√	√	√	
Distance Visual Acuity	✓		√	√	✓	√	
Microperimetry	√				✓	√	
Schirmer Test	√				✓	√	
SD-OCT	√		✓	✓	✓	✓	
Wide-angle FFA	✓				✓		
Blood sample for ARA 290 antibodies, immune markers, carbamylated and glycosylated albumin	✓				✓		
Blood sample for full blood cell count	~				√	✓	
Liver function test (LFT)	~				✓	√	
Urine Sample	✓				✓	✓	
Adverse Events		✓	√	✓	✓	√	✓
VFQ-25	~				✓	√	
EQ-5D-5L	~				✓	√	
C-SSRS	~		✓	✓	✓	√	
Telephone check		√					✓

- * 16 week visit will take place only if the retina is found to be dried and the DMO has resolved at week 12
- ** 4 week post study drug termination telephone check will be completed for patients who withdraw from the trial/study drug prior to 12 weeks, or at 12 weeks, and who do not need to attend the 16 week visit.
- *** Vital signs: height (first visit only); weight; heart rate; temperature; blood pressure, oxygen saturation, BMI

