5. SAMPLE SIZE CALCULATIONS

This will be an early phase, open label, interventional pilot study to evaluate the potential beneficial effect of ARA 290 for the treatment of patients with DR and DMO and further assess the safety of this treatment. Ten patients will be recruited. A sample of this size is expected to be sufficient to provide an indication of a potential beneficial effect of the drug on the outcomes investigated and further information on safety of ARA 290 in a diabetic population. Data obtained in this study will be used to inform future larger studies.

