7.5 Toxicity/ Symptoms

- Adverse Events (AEs), Serious adverse events (SAEs), related AEs and SAES, AEs and SAEs that led to study discontinuation, and Suspected unexpected serious adverse reactions (SUSARs)
- Mortality

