Appendix 1: Summary Tables

Table 1. Baseline and Week 12 Characteristics

Characteristics		ARA290-DMO	Week 12
		n= <n></n>	n=(%)
Gender	Male	n(%)	-
	Female	n(%)	-
Study Eye	Left	n(%)	-
	Right	n(%)	-
Type of diabetes	Type 1	n(%)	-
	Type 2	n(%)	-
Age (years)		$xx.x \pm xx.x$	$xx.x \pm xx.x$
Weight (kg)		$xx.x \pm xx.x$	$xx.x \pm xx.x$
Height (m)		$xx.x \pm xx.x$	-
BMI (kg/m2)		$xx.x \pm xx.x$	-
Systolic Blood pressure (mm	Hg)	$xx.x \pm xx.x$	$xx.x \pm xx.x$
Diastolic Blood Pressure		$xx.x \pm xx.x$	$xx.x \pm xx.x$
Heart rate (bpm)		$xx.x \pm xx.x$	$xx.x \pm xx.x$
Temperature (degrees celsiu	ıs)	$xx.x \pm xx.x$	$xx.x \pm xx.x$
Oxygen saturation (%)		$xx.x \pm xx.x$	$xx.x \pm xx.x$
C peptide (ng/ml)		$xx.x \pm xx.x$	$xx.x \pm xx.x$
HbA1c (mmol/L)		$xx.x \pm xx.x$	$xx.x \pm xx.x$
Glucose (mmol/L)		$xx.x \pm xx.x$	$xx.x \pm xx.x$
HDL (mmol/L)		$xx.x \pm xx.x$	$xx.x \pm xx.x$
LDL (mmol/L)		$xx.x \pm xx.x$	$xx.x \pm xx.x$
Triglycerides (mmol/L)		$xx.x \pm xx.x$	$xx.x \pm xx.x$
Albumin Creatine Ratio		$xx.x \pm xx.x$	$xx.x \pm xx.x$
Liver Function Test	AST(mmol/L)	$xx.x \pm xx.x$	$xx.x \pm xx.x$
(LFT)	ALT(mmol/L)	$xx.x \pm xx.x$	$xx.x \pm xx.x$

Mean ±SD presented for continuous variables (or median [interquartile range] when appropriate) and no. (%) for all categorical variables.

Data listings for characteristics including co-morbidities and ophthalmologic condition will be included as an appendix in the final statistical report.

Table 2. Treatment after Trial Entry

Treatment after Trial Entry	ARA290-DMO
Treatment after Trial Entry	n = (%)
Study drug given	n(%)
Number of doses administered*	xx.x ± xx.x
Reasons for early termination of study drug	
Adverse Event	n(%)
Serious Adverse Event	n(%)
Protocol Deviation	n(%)
Other	n(%)
Protocol violations:	
Eligibility	n(%)
Study Drug Administration	n(%)
Visit out of schedule	n(%)
Other	n(%)

^{*}patients are expected to have received 120 doses over 120 days.

Table 3.1 Main Clinical Outcome variables

		Study Eye					Non-Study Eye						
		Base	line	Weel	k 12	Chang	je	Base	line	Weel	k 12	Cha	nge
		n =	(%)	n = ((%)	n = (°	%)	n =	(%)	n = ((%)	n =	(%)
•	tcome; best distance visual	· · · · · · · · · · · · · · · · · · ·		xx.x ± xx.x									
Central sub thickness (xx.x ± xx	.x	xx.x ± xx	.x	xx.x ± xx.x		xx.x ± xx	x	xx.x ± xx	.x	xx.x ± xx.x	
Central reti	inal sensitivity	xx.x ± xx	.x	xx.x ± xx	.x	xx.x ± xx.x		xx.x ± xx	.x	xx.x ± xx	.x	xx.x ± xx.x	

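### The SAP has no value-based safety summary of ALT/AST or vital signs, and vital signs from weeks 4 and 8 have no named output

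*SAP*

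**What the plan says.** **Purpose and size.** SAP 5 and Protocol 12.1 name further assessment of safety as a purpose. The sample is small: "Ten patients will be recruited". Protocol 3.3 says that treatment for 84 days is new; most previous studies used 28 days.

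**What is collected.** The schedule in SAP 3.2 has liver tests at baseline and week 12, and vital signs at baseline and weeks 4, 8 and 12. The items are defined as "Vital signs: height (first visit only); weight; heart rate; temperature; blood pressure, oxygen saturation, BMI". SAP 4 defines the liver tests as ALT and AST. A week 16 visit was conditional, and SAP 6 records that no patient needed one.

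**What is summarised.** SAP 7.2 lists "Liver Function Test, mean(sd") and "Blood Pressure(mmHg), mean(sd) systolic, diastolic" among the baseline characteristics. The matching shell is "Table 1. Baseline and Week 12 Characteristics", with the note "Mean ±SD presented for continuous variables (or median [interquartile range] when appropriate"). SAP 6 gives the switching rule: "When data is not normally distributed, median (interquartile range) will be presented".

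**The safety section.** SAP 7.5 lists "Adverse Events (AEs), Serious adverse events (SAEs), related AEs and SAES, AEs and SAEs that led to study discontinuation", then SUSARs and mortality. Neither SAP 7.4 nor SAP 7.5 has a liver or vital-sign item.

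**Other routes to individual values.** A note under Appendix Table 1 promises data listings for characteristics. Table 4.2 has patient-count rows for hypertension, raised GGT and abnormal blood test results, and adverse event listings are promised below it.

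**The concern.** In ten patients, an effect on the liver or on blood pressure is more likely to appear as one or two individuals out of range than as a shift of the group. Means, SDs, medians and quartiles describe the group. The summaries that identify individuals are the range, the count beyond a limit, the shift from baseline category and the largest individual change. None of them is planned for ALT, AST or vital signs.

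Two features add to this. Two of the three on-treatment vital-sign visits feed no named output, so a rise at week 4 or 8 that had settled by week 12 would leave no trace in the tables unless it was reported as an adverse event. And the rule in SAP 6 selects the more resistant summary precisely when one value lies far from the rest. For an efficacy variable that is a reasonable default. For a safety variable it discards the observation of interest.

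At stake is whether the report can support a statement about liver and haemodynamic safety over 84 days from the measured values, rather than from adverse event reports alone.

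**Working it through.** The documents give no figure to reproduce: the sample size has no calculation behind it and the analysis is descriptive. The check is a trace of outputs, followed by an illustration.

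**1. Trace of outputs**

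| Data | Visits scheduled (to week 12) | Value-based summary in the SAP |
|---|---|---|
| ALT, AST | baseline, week 12 | Appendix Table 1, baseline and week 12 |
| Vital signs | baseline, weeks 4, 8, 12 | Appendix Table 1, baseline and week 12 (BMI and height at baseline only) |

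Table 1 has no change column, range, threshold count or shift. Weeks 4 and 8 are named in no shell and no listing. Liver tests are not scheduled at those visits, so that gap concerns vital signs alone.

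On-treatment vital-sign visits: 10 patients × 3 visits = 30. Without named output: 10 × 2 = 20. Share: 20/30 = 67%. This assumes that all ten patients attend every visit.

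**2. One liver outlier among ten**

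The documents give no ALT distribution and no upper limit. Assumed baseline values: 15, 18, 20, 22, 24, 26, 28, 30, 32, 35. Assumed upper limit: 40. The patient at 24 is changed to 120 (3 × 40) or 200 (5 × 40).

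- Mean: 250/10 = 25.0; (250 − 24 + 120)/10 = 34.6; (250 − 24 + 200)/10 = 42.6.
- Median: (24 + 26)/2 = 25; with either outlier (26 + 28)/2 = 27.

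| | Mean | SD | Median | IQR |
|---|---|---|---|---|
| Baseline | 25.0 | 6.4 | 25 | 20.5–29.5 |
| One at 120 | 34.6 | 30.7 | 27 | 20.5–31.5 |
| One at 200 | 42.6 | 55.7 | 27 | 20.5–31.5 |

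The SD reacts strongly. The median and IQR barely move, and they are identical for 120 and 200. If the affected patient is instead the one who started highest (35), the median and IQR do not move at all: 25 and 20.5–29.5.

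**3. Would the switch occur?** The SAP names no normality test. If Shapiro-Wilk were used, p would be about 2 × 10⁻⁵ with the value 120 and 2 × 10⁻⁶ with 200, so either outlier would trigger the median.

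**4. One blood-pressure rise among ten**

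The shift in the mean is the rise divided by 10: rises of 20, 30 and 40 mmHg move it by 2, 3 and 4 mmHg. With an assumed baseline of 140 (SD 15) at normal-score spacing, the median lies between 140 and 142 in all three cases. The SD becomes 16.5–19.4, 18.1–21.9 and 20.0–24.6, depending on whether the patient started mid-range or highest. The hint from the SD is much weaker here than for ALT.

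**5. What a count would show.** One affected patient is 1/10 = 10%, exact 95% interval 0.3% to 44.5%. The estimate is imprecise, but the patient is visible.

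**The case against.** A reader might infer that these data appear only as group means, or that one patient's signal cannot be seen anywhere in the planned safety output. The documents do not support either reading:

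- **Adverse event tables.** Table 4.2 counts patients with hypertension, raised GGT and abnormal blood test results. Table 4.1 has rows for vascular disorders and investigations. Adverse event listings are planned, and Protocol 13.2 requires all directly observed events to be recorded.
- **Listings of characteristics.** The note under Table 1 is worded inclusively. In ten patients, a listing is a patient-level display.
- **The SD.** A large ALT outlier raises it more than fourfold, so mean ± SD beside the baseline column would prompt a question.
- **The switch.** No normality test is named, and Table 1 leaves the choice of statistic to judgement.
- **Scope.** The protocol's safety outcome is adverse events, reported as counts and percentages. The DMEC reviews safety data about every four weeks, so oversight of participants does not depend on Table 1.

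All of this stands, and it limits the point. It does not remove it. The adverse event rows depend on investigator reporting in an open-label trial, and neither document states a value at which a laboratory result or vital sign becomes an adverse event. GGT is not among the liver tests that the SAP defines, and no row is specific to ALT or AST. The listings do not name liver tests, vital signs or weeks 4 and 8, and no flagging is specified. The SD hint is lost if the median is shown, and for blood pressure it is modest at best. The documents do not say that the DMEC's safety data include laboratory values or vital signs, and DMEC review is in any case separate from what the final report shows.

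**Conclusion.** The point holds as a gap in systematic, value-based safety reporting. ALT, AST and vital signs are summarised only in the characteristics table, at baseline and week 12, by group statistics. Twenty of 30 scheduled on-treatment vital-sign visits have no named output. A one-patient signal would show in unflagged listings, through an inflated SD, or in Tables 4.1 and 4.2 if it was reported as an adverse event. Under the median [IQR] option it would be close to invisible in the summary.

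The text trace rests on no assumption. The size of the masking does: the ALT values, the upper limit of 40, the blood-pressure distribution and the Shapiro-Wilk trigger are illustrative. That the median and IQR come out the same at 120 and 200 does not depend on the limit chosen.

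This is a change that should be made because safety is a stated purpose. It does not affect the primary outcome or the conduct of the trial.

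**What to change.** Add one table to SAP 7.5 containing:

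1. the number of patients with ALT or AST above the laboratory upper limit, and above multiples of it that the trial team sets in advance, at baseline and week 12, laid out as a shift table;
2. each patient's largest change from baseline in systolic pressure, diastolic pressure and heart rate over weeks 4, 8 and 12;
3. the minimum and maximum beside any mean or median of these variables, in this table and in Appendix Table 1.

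The cost is one table. The measurements are already scheduled, and nothing changes in the visits or the efficacy analysis. The documents do not show that laboratory reference ranges are held in the trial database. If they are not, they must be obtained from the laboratory before item 1 can be produced.
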